2.4 Determination of sample size

2.4.1 Power calculations for the primary endpoint

The sample size assumptions for BKZ versus placebo are based on the ACR50 response data from the Phase 2b BKZ study in subjects with moderate-to-severe PsA (PA0008). The median ACR50 responses of the top 3 dose groups (BKZ 160mg, 320mg, and 320mg [initial dose] plus 160mg) at Week 12 in the Tumor necrosis factor-naïve (TNF-naïve) population are conservatively assumed for the Week 16 endpoint. The observed median ACR50 response rate of the top 3 BKZ doses in the TNF-naïve population in study PA0008 was 43.8%.

The placebo ACR50 response at Week 16 is based on the TNF α -naïve population in PA0008 (6.1% at Week 12, subjects with available measurement (n)=33); Mease et al, 2015), FUTURE 2 study in the subgroup of TNF α -naïve subjects (15.9%, n=63; McInnes et al, 2015), FUTURE 3 study (11.8%, n=93; Nash and Mease, 2018), and FUTURE 5 study in a mixed tumor necrosis factor alpha (TNF α) exposure population (8.1% at Week 16, n=332; Mease et al, 2018). Therefore, the estimated ACR50 response at Week 16 in the placebo group is assumed to be 16%.

The sample size for showing statistical superiority of BKZ vs placebo was calculated using a 2-sided 2-sample Chi-square test with continuity correction (Fleiss et al, 1980). Assuming 420 subjects in the BKZ group and 280 subjects in the placebo group, the test for detecting statistical superiority of BKZ 160mg Q4W vs placebo based on ACR50 response at Week 16 has >99% power to detect a true treatment difference of 27.8% (odds ratio (OR) 4.09).

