3.2.2 Mapping of assessments performed at Early Discontinuation Visit

Study assessments at an early termination visit where visit date matches the visit date of a scheduled visit will be summarized at the scheduled visit with the same visit date. Premature study termination visit assessments that do not have a scheduled visit with a matching date will be assigned a visit based on the protocol-defined visit windows (± 2 days up to and including Week 16, and ± 3 days from Week 20 up to and including Week 52). For early discontinuation visits that fall between protocol defined visit windows and not within them, the later of the 2 visits is assigned.

If there is an existing scheduled site visit in the window, then the assessments at the ET visit will be mapped to the next scheduled site visit.

The ADAb assessments, PK and the vdHmTSS are exceptions to this rule:

- ADAb levels, PK from an early termination visit will be mapped to the next visit where they are measured.

- VdHmTSS from an early termination visit will be mapped to the Week 16 assessment (if the early termination is before Week 16) or to the Week 52 assessment (if the early termination is between Week 16 and Week 52).

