- If subjects have missing data regardless of whether the missing data is preceded by an IE, then missing data will be imputed based on the MI-Markov-Chain Monte Carlo (MI-MCMC) /Reference-Based imputation method ([Section 4.2.2.3](#)).
- If subjects have non missing data after IE, then such data will be set to missing prior to running MI.

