No formal alterations to the further study conduct (eg, stopping rules, sample size re-estimation, or changes to eligibility criteria) are planned for the 2 interim analyses.

No separate SAP for the interim analyses will be provided. The TFL shells for the interim and the final analyses will be provided in the same document and appropriately identified.

The below table summarize the type of efficacy and safety analyses to be performed for the 2 interim analyses.

Table 4-4: Type of efficacy and safety tables provided for the interim analyses

Variable Type of tables	Period or Timepoint (Analysis set)	Treatment groups	Provided for Interim Analysis 1 (Week 24 analysis)	Provided for Interim Analysis 2 (Week 52 analysis)
Tables of primary efficacy variable	Week 16 (RS FAS PPS)	
 • Placebo • BKZ 160mg Q4W • ADA 40mg Q2W 	Yes	Yes, rerun of tables provided for interim analysis 1
Tables of secondary efficacy variables.	Week 4 and 16 (RS*)	
 • Placebo • BKZ 160mg Q4W • ADA 40mg Q2W 	Yes	Yes, rerun of tables provided for interim analysis 1
Tables / Graphs of time to ACR response	DBP (RS)	
 • Placebo • BKZ 160mg Q4W • ADA 40mg Q2W 	Yes, subjects not achieving response at Week 16 are censored at Week 16.	Yes, rerun of tables provided for interim analysis 1
	Overall Study Period (RS)	
 • Placebo/BKZ 160 mg Q4W • BKZ 160mg Q4W • ADA 40mg Q2W 	Yes, subjects not achieving response at Week 24 are censored at Week 24.	Yes, subjects not achieving response at Week 52 are censored at Week 52.
By-visit tables of other efficacy endpoints	Overall Study Period (RS*)	
 • Placebo / BKZ 160 mg Q4W • BKZ 160mg Q4W • ADA 40mg Q2W 	Yes, from Baseline to Week 24	Yes, from Week 0 until Week 52.
Extra by-visit tables for ACR50 and PASI90 using Baseline Week 16	ATP (ATS)	
 • Placebo / BKZ 160mg Q4W 	Yes, from Week 20 until Week 24	Yes, from Week 16 until Week 52.
Extent of exposure and time at risk	DBP (SS)	
 • Placebo • BKZ 160mg Q4W • ADA 40mg Q2W 	Yes	Yes
	ATP (ATS)	
 • Placebo / BKZ 160mg Q4W • BKZ 160mg Q4W • BKZ 160mg Q4W Total • ADA 40mg Q2W 	Yes, until Week 24	Yes

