4.5 Multiple comparisons/multiplicity

A step-down closed testing procedure will be applied for the primary endpoint and some secondary endpoints. The testing procedure will account for multiplicity and control the family-wise type I error rate at alpha=0.05 (2-sided).

For each test, on each binary efficacy endpoint, the null hypothesis is that the conditional odds ratio is equal to one ($H_0: OR_{T1T2} = 1$). The alternative hypothesis is that the conditional odds ratio is not equal to one ($H_A: OR_{T1T2} \neq 1$).

For each test, on each continuous efficacy endpoint, the null hypothesis is that there is no difference between treatment groups ($H_0: T_1 - T_2 = 0$). The alternative hypothesis is that there is a difference between treatment groups ($H_A: T_1 - T_2 \neq 0$).

T_1 refers to BKZ and T_2 to placebo.

According to this strategy, the statistical testing of an endpoint can be investigated only if the null hypothesis for the previous endpoint has been rejected (i.e., if $p < 0.05$). [Table 4-5](#) shows the testing order for these endpoints.

Table 4-5: Sequential testing procedure of primary/secondary efficacy endpoints (fixed sequence testing procedure) (All efficacy endpoints at Week 16)

BKZ 160mg Q4W	
H_1	ACR50 Response superior to Placebo
H_2	Change from Baseline HAQ-DI superior to Placebo

BKZ 160mg Q4W	
H ₃	PASI90 Response superior to Placebo
H ₄	Change from Baseline SF-36 PCS superior to Placebo
H ₅	MDA superior to Placebo
H ₆	Change from Baseline vdHmTSS* superior to Placebo on subjects with elevated hs-CRP and/or with at least one bone erosion (hs-CRP ≥ 6 mg/L and/or erosion-positive)
H ₇	Enthesitis-free state superior to Placebo (based on pooled PA0010 and PA0011 W16 data)
H ₈	Dactylitis-free state superior to Placebo (based on pooled PA0010 and PA0011 W16 data)
H ₉	Change from Baseline vdHmTSS** superior to Placebo

ACR=American College of Rheumatology; BKZ=bimekizumab; CfB=change from Baseline; H=hypothesis;

HAQ-DI=Health Assessment Questionnaire - Disability Index; hs-CRP=high sensitivity C-reactive protein;

LEI=Leeds Enthesitis Index; MDA=Minimal Disease Activity; PASI=Psoriasis Area and Severity Index.

PCS=Physical Component Summary; Q4W=every 4 weeks; SF-36=Short-Form 36-item Health Survey;

vdHmTSS=Van der Heijde modified Total Sharp Score.

* It is planned to enroll a minimum of 45% of subjects who are positive for elevated hs-CRP (hs-CRP ≥ 6 mg/L) and/or who have at least 1 bone erosion at Screening.

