- If the total score is missing at a post-Baseline visit (ie, only "N" or "S" is recorded for all joints) or if JSON or ES score is missing then the missing total score will be imputed using MI imputation.

For the change from Baseline analyses, subjects who withdraw early and have radiographs taken at their early withdrawal visit should be included in the analysis. In such cases, one or more imputation methods may be applied for the subjects with less than 2 radiographs. In addition to any such imputation approach that is selected, an analysis excluding subjects with less than 2 radiographs from the analysis should be performed.

In the testing hierarchy (Table 4-5), 2 endpoints are defined based on the vdHmTSS:

- Change at Week 16 from Baseline in vdHmTSS for subjects with elevated hs-CRP and/or with at least one bone erosion at Baseline (planned to be approximately 45% of the overall population). This is the 6th endpoint in the sequential testing hierarchy.
- Change at Week 16 from Baseline in vdHmTSS for all subjects. This is the 9th endpoint in the sequential testing hierarchy.

The 2 endpoints will be analyzed in the radiographic set.

At Week 16, imaging data collected outside ± 14 days of the expected visit date will be excluded from the analysis.

For the Week 24 interim analysis only, in the primary analysis of these 2 endpoints, missing data at Week 16 will be imputed based on value at Screening (as there is no value collected in between) using MI-MCMC / Monotone regression. Since VdHmTSS is only collected at Baseline prior to Week 16, only the second MI step to address monotone missing pattern and generating 100 imputations will be processed (Section 4.2.2.2).

8.2.1.6 Enthesitis-free state at Week 16 in the subgroup of subjects with enthesitis at Baseline

The Leeds Enthesitis Index (LEI) consists of 6 items, 3 for the right part and 3 for the left part of the body. The body parts are Lateral epicondyles of the humerus, Medial femoral condyle, and

Achilles tendons. Each item is scored for tenderness with either 1 or 0 (tenderness, no tenderness, respectively). The total score ranges from 0 (no enthesitis) to 6 (severe enthesitis).

Note that LEI is collected for all subjects regardless of their Baseline score.

In case 4 items are missing, the LEI will be set to missing. If at least 3 items are available, the available items will be assessed and scored and then weighted by the number of the assessed items (AI) as shown in the formula below:

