- Population-level summary measure = the difference in the adjusted means between BKZ 160mg Q4W and placebo.

The same analysis model and imputation strategy for handling missing data as in [Section 8.1.4.4](#) will also be considered. The analysis results will be presented similarly as for this analysis on the individual ACR components.

For vdHmTSS, a similar estimand structure as the one defined above for continuous endpoints will be used with the following exception for population:

- When analyzing change at Week 16 from Baseline in vdHmTSS for subjects with elevated hs-CRP or with at least one bone erosion at Baseline: Population=Subjects enrolled according to the protocol-specified inclusion/exclusion criteria, randomized to IMP, who have a valid radiographic image of the hands and feet at Baseline in the subgroup of patients with elevated CRP and with at least one bone erosion at Baseline.

- When analyzing change at Week 16 from Baseline in vdHmTSS for all subjects:
Population=Subjects enrolled according to the protocol-specified inclusion/exclusion criteria, randomized to IMP, who have a valid radiographic image of the hands and feet at Baseline.

In the case of MDA as the response is based on 7 different component scores, it is necessary to consider various data scenarios that could impact the calculation of response. The rules described here are applicable in the context of the calculation of MDA response and may differ from the rules applied for calculating and summarizing the components individually (some values may need to be imputed for component analysis but are not required here to evaluate MDA response).

The following rules will be applied to complete the derivation of MDA response based on the composite estimand definition:

- If a given visit has been preceded by an IE (treatment discontinuation):
 - The endpoint at all subsequent visits (whether the data were observed or not) will be set to “non-response” as the subject has not met the criteria for response.
- If a given visit has not been preceded by an IE:
 - If a subject is satisfying at least 5 of the 7 MDA criteria, the subject will be considered as MDA responder
 - If a subject is not satisfying at least 3 MDA criteria, the subject will be considered as MDA non-responder
 - In all other cases, the NRI approach will be applied.

An overview table will combine the results of the primary analysis for the primary and secondary efficacy endpoints included in the testing hierarchy.

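### H6 and H9 (vdHmTSS change at Week 16) have two stated primary imputation methods at the Week 24 analysis, and the method for the Week 52 rerun is not stated

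*SAP*

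**What the plan says.** H6 is the Week 16 change in vdHmTSS in subjects with raised hs-CRP and/or bone erosion. H9 is the same change in all subjects (Table 4-5). Both are analysed in the Radiographic Set.

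**Method A, Section 8.2.1.5.** "For the Week 24 interim analysis only, in the primary analysis of these 2 endpoints, missing data at Week 16 will be imputed" from the Screening score by MI-MCMC/monotone regression. Only the monotone step is run, because no film is scheduled in between. Section 4.2.2.2 defines this method as MAR and fits it in each treatment group separately.

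**Method B, the general rule.** Section 4.2.1.2, on continuous hierarchy endpoints: "then missing data will be imputed based on the MI-Markov-Chain Monte Carlo (MI-MCMC) /Reference-Based imputation method". Sections 3.10, 4.2.2.3 and 8.2.2 say the same, and Table 4-2 marks it as the primary method. Section 8.2.2 then takes up the X-ray score by name: "For vdHmTSS, a similar estimand structure as the one defined above for continuous endpoints will be used with the following exception for population". Section 4.2.1.4 and Table 4-2 list monotone-regression MI as supportive.

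**Later reports.** Table 4-4 describes the Week 52 secondary-endpoint tables as "Yes, rerun of tables provided for interim analysis 1". Section 4.5 sets up the fixed sequence to "control the family-wise type I error rate at alpha=0.05 (2-sided") but does not say which report decides it.

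**Films.** Section 3.2.2: "VdHmTSS from an early termination visit will be mapped to the Week 16 assessment (if the early termination is before Week 16"). Section 8.2.1.5 asks that early-withdrawal films be included, and also says: "At Week 16, imaging data collected outside ± 14 days of the expected visit date will be excluded from the analysis".

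**The concern.** A confirmatory test needs one prespecified primary analysis. Here the estimate, and possibly the verdict, depends on which section the programmer follows. The two methods answer different questions. Within-arm MAR MI treats a bimekizumab subject with a missing film as having continued like other bimekizumab subjects. Placebo-reference MI treats that subject as having progressed like placebo.

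Section 4.3.1 says the Week 24 analysis is the basis for the marketing application. H6 also gates H7 (enthesitis), H8 (dactylitis) and H9, so an open choice at H6 carries down the sequence. The film rules matter because they decide who is imputed at all.

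**Working it through.** **1. The sections side by side, at Week 24**

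| Source (SAP) | Primary imputation for H6/H9 | vdHmTSS or Week 24 exception? |
|---|---|---|
| 8.2.1.5 | Within-arm monotone-regression MI (MAR) | Is itself the exception |
| 3.10, 4.2.1.2, 4.2.2.3, Table 4-2 | Reference-based MI | None |
| 8.2.2 | Reference-based MI | vdHmTSS named; only the population differs |

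Three things follow.
- The 8.2.2 estimand treats subjects who stop as if they had completed on placebo. Section 8.1.4.4 lists completion of treatment and completion on placebo as two separate strategies, (a) and (b). Method A belongs to (a), while the stated estimand is (b). Section 8.2.2 also refers back to 8.1.4.4, which runs both methods in turn, so that reference does not settle the matter.
- If Method A is primary, it coincides with the supportive method in 4.2.1.4 and 8.2.3, and the contrast between two MI methods is lost.
- The absence of films between Screening and Week 16 explains skipping the MCMC step. It does not explain leaving the placebo-based model, because the sequential algorithm in 4.2.2.3 can run on Screening and then Week 16.

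**2. Reproducing the plan's power**

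Inputs:
- Section 2.4.1: "Assuming 420 subjects in the BKZ group and 280 subjects in the placebo group".
- Section 2.4.2, H6: means 0.06 vs 0.36, SD 0.720 vs 0.710, 45% of subjects, so 0.45 × 420 = 189 and 0.45 × 280 = 126.
- Section 2.4.2, H9: difference 0.42, SD 1.13 vs 2.44.
- Two-sided Satterthwaite t-test, alpha 0.05, noncentrality = difference/SE.

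Results:
- H6: SE = √(0.72²/189 + 0.71²/126) = 0.0821; 0.30/0.0821 = 3.65; power 95.4% (plan: 95%).
- H9: SE = √(1.13²/420 + 2.44²/280) = 0.156; 0.42/0.156 = 2.69; power 76.6% (plan: 76%).

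Table 2-1 also reproduces, to within about 1.2 points.

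**3. Size of the difference between methods**

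The SAP gives no missing-film rate, so let an assumed share m be missing in each arm, at random. Under within-arm MAR MI the expected difference stays at δ. Under reference-based MI the missing bimekizumab subjects take the placebo mean, so the difference becomes (1−m)δ. For H6 at m = 10%: 0.9 × 0.06 + 0.1 × 0.36 = 0.090, and 0.090 − 0.36 = −0.270.

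Precision is taken as that of the completers, n(1−m), under both methods. For H6 at 10%, SE = 0.0821/√0.9 = 0.0866, and the noncentrality is 0.30/0.0866 = 3.47 against 0.27/0.0866 = 3.12.

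| Missing per arm (assumed) | H6 effect, MAR / ref. | H6 power, MAR / ref. | H9 effect size, MAR / ref. | H9 power, MAR / ref. |
|---|---|---|---|---|
| 5% | −0.30 / −0.285 | 94.4 / 92.1% | 0.42 / 0.399 | 74.5 / 70.1% |
| 10% | −0.30 / −0.270 | 93.2 / 87.4% | 0.42 / 0.378 | 72.2 / 63.1% |
| 15% | −0.30 / −0.255 | 91.8 / 81.4% | 0.42 / 0.357 | 69.7 / 55.8% |

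A simulation checked this (1,000 trials, 100 imputations, Rubin's rules, pooled variance, no covariates). At 5, 10 and 15% missing the two methods gave different significance verdicts in 1.3, 3.5 and 6.5% of trials for H6, and 4.6, 11.1 and 18.9% for H9. In every discordant trial only MAR MI was significant. For H6 the simulated reference-based power was 92.8, 89.3 and 84.2%, so the table somewhat overstates the H6 loss.

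**4. Films**

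Take a subject who terminates early with a film at Week 6. Section 3.2.2 maps it to Week 16, and one sentence of 8.2.1.5 includes it. Another sentence of 8.2.1.5 excludes it, because it lies 10 weeks (70 days) from the expected date, outside ±14 days.

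**The case against.** The strongest reply is that 8.2.1.5 is a deliberate, specific exception that overrides a general rule. The change log in Section 13.3 shows that monotone-regression MI was already primary for these two endpoints before the Week 24 restriction was added. That stands as history, and it is a reason not to delete the sentence outright. It does not remove the conflict: 8.2.2 deals with vdHmTSS by name and excepts only the population.

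A reader might infer that the Week 52 analysis switches to reference-based MI and could reverse a claim already made. The documents do not support that as fact. No section says so; it follows only by default once the Week 24 restriction lapses, and Table 4-4 calls the tables a rerun. The restriction may also be technical. At Week 52 a missing Week 16 film followed by a Week 52 film is intermittent, so skipping the MCMC step would no longer be valid. Nor does any section provide for a second pass through the hierarchy, and Section 4.3.1 has Week 52 supplement the submission.

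A reader might also infer that the Week 24 method inflates type I error. The calculation shows only a larger expected effect when the drug truly works.

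**Conclusion.** The point holds for Week 24: two confirmatory tests have two stated primary imputations, and the one in 8.2.1.5 does not fit the estimand in 8.2.2. For Week 52 the finding is only that the method is unstated.

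The estimates will differ whenever bimekizumab films are missing. Whether the verdict differs depends on the missing rate, which is an assumption here. At 5% the power gap is about 2 points for H6 and 4 for H9. At 10% it is about 6 and 9. These figures rest on the plan's effect sizes, equal random missingness in both arms, and completer-level precision. H6 is the better powered of the two but gates H7 to H9. H9 is more sensitive but is last and gates nothing.

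The film rules are a separate, genuine conflict. Including early-withdrawal films would lower the missing rate that drives these gaps.

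**What to change.** - Name one primary imputation for H6 and H9, use it at every reporting event, and show the other beside it as supportive. Reference-based MI is the one that matches the stated estimand.
- If monotone-regression MI is kept as primary, write the vdHmTSS exception and a matching estimand into 3.10, 4.2.1.2, Table 4-2 and 8.2.2.
- If the Week 24 analysis has already been run under 8.2.1.5, keep that text on record and report both methods. Replacing it could change a confirmatory method after unblinding.
- State in 4.5 that the hierarchy is decided once, at the Week 24 analysis, and that later reruns are descriptive.
- Separately, reconcile 3.2.2 with the two statements in 8.2.1.5 so that a single rule decides which films count as Week 16. A ±14-day limit applied to early-termination films is one option, not the only one.

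The cost is SAP wording and one extra run of two tables. The H6 and H9 estimates may become slightly less favourable.

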BASDAI=Bath Ankylosing Spondylitis Disease Activity Index; EQ-5D-3L=Euro-Quality of Life 5-Dimensions 3 Level version; FACIT=Functional Assessment of Chronic Illness Therapy; HAQ-DI=Health Assessment Questionnaire – Disability index; hs-CRP=High sensitivity C-reactive protein; IGA=Investigator Global Assessment; LDI=Leeds Dactylitis Index; LEI=Leeds Enthesitis Index; LLOQ=lower limit of quantification; mNAPSI=Modified Nail Psoriasis Severity Index; PASI=Psoriasis Area and Severity Index; PGA-Arthritis=Patient's Global Assessment of Arthritis; PGA-PsA=Patient's Global Assessment of Psoriatic Arthritis; PhGA-Arthritis=Physician's Global Assessment of Arthritis; PhGA-PsA=Physician's Global Assessment of Psoriatic Arthritis; PHQ-9=Patient Health Questionnaire-9; PSAID-12=Psoriatic Arthritis Impact of Disease-12; PsAQoL=Psoriatic Arthritis Quality of Life; PtAAP=Patient's Assessment of Arthritis Pain; SF-36=Short-Form 36-Item Health Survey; SJC= swollen joint count; SPARCC= Spondyloarthritis Research Consortium of Canada ; TJC=tender joint count; vdHmTSS=van der Heijde Modified Total Sharp Score; WPAI-SHP=Work Productivity and Activity Impairment Questionnaire – Specific Health Problem

^aminimum and maximum of the norm-based scores – Normal range for SF-36 scores is 0-100

4.2.1.1 Primary analysis of binary endpoints that are part of the testing hierarchy (primary and secondary endpoints)

All binary endpoints (composite & non-composite) are based on continuous component variables.

The primary analysis of binary efficacy endpoints that are part of the testing hierarchy is considered under an estimand framework in which missing data (due to study treatment discontinuation) is considered indicative of failed treatment and imputed to non-response. Further missing data for subjects on treatment, or data observed while not on treatment is also imputed to non-response.

This composite estimand approach to handling missing data which is the primary analysis method for binary efficacy endpoints is similar to the non-responder imputation (NRI) method.

4.2.1.2 Primary analysis of continuous endpoints that are part of the testing hierarchy (secondary endpoints)

For continuous efficacy endpoints that are part of the testing hierarchy, the primary analysis method is based on the hypothetical estimand approach as follows:

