
$$LEI = n \times \frac{\sum_{i=1}^n score}{\sum_{i=1}^n AI}$$

Note that n here refers to the number of total items.

Enthesitis-free state is based on a LEI response of 0 at Week 16, for subjects with enthesitis at Baseline (LEI>0).

Enthesitis-free state at Week 16 (pooled between PA0010 and PA0011) is the 7th endpoint in the sequential testing hierarchy (Table 4-5) and will be based on pooled data from PA0010 and PA0011 (for subjects in the BKZ160mg Q4W and the Placebo groups). The analysis will also be repeated using PA0010 data alone and the p-value for this analysis will only be considered nominal.

8.2.1.7 Dactylitis-free state at Week 16 in the subgroup of subjects with dactylitis at Baseline

The LDI measures the percent difference between the circumference of the affected digit and the circumference of the digit on the opposite hand or foot (referred to as the contralateral digit), where circumference is measured in millimeters. A minimum difference of 10% and the assessment of the investigator that the digit was affected by dactylitis will be used to define a dactylitis digit.

The percent difference between circumferences will be multiplied by a tenderness score (0 for non-tender, 1 for tender). The score using the binary tenderness score is referred to as the LDI basic. The results from each digit with dactylitis will then be summed to produce a final LDI score.

Table 8-3 is a table of normative values, which will be used to provide the comparison, if matching digits are thought to be involved.

Table 8-3: Normative values for LDI

	Digit	Men	Women
Hand	Thumb	70	58
	Index	63	54
	Middle	63	54
	Ring	59	50
	Little	52	44
Foot	Great toe	82	72

	Digit	Men	Women
	Second	52	46
	Middle	50	44
	Fourth	50	44
	Little	52	45

The following rules will be applied for the LDI calculation in case of unclear data.

- Circumferences of 0 will be considered as missing. Circumferences <15 will be assumed to be in cm instead of mm and will be multiplied by 10 before being used in summaries/analyses.
- If both digits of a given pair are recorded as affected, then each digit will be compared to the normative value (shown in the above table). Note that if both comparisons result in a difference $\geq 10\%$, then both digits will contribute to the final LDI score.
- If the circumference of the affected digit is smaller than the unaffected digit, then the LDI will be calculated by comparing the smaller digit to the normative value.

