4	Severe	Severe thickening with hard edges; bright to deep dark red coloration severe/coarse scaling covering almost all or all lesions

IGA=Investigator's Global Assessment; PSO=psoriasis

The IGA response is defined as clear [0] or almost clear [1] assessment with at least a 2-category improvement from Baseline, meaning that this parameter will be only evaluable for subjects with psoriatic skin lesions (IGA score ≥ 2) at Baseline.

Note that per protocol and device setting, only subjects with BSA $\geq 3\%$ at Baseline will have IGA assessed at post-Baseline visits.

For some subjects with BSA $\geq 3\%$ at Baseline, IGA data have not been captured at Week 4 and Week 16 visits when BSA $< 3\%$ at those visits. To address that, an additional supportive analysis will be performed in which these subjects will be considered as IGA responders at the respective visit.

8.2.1.11 Change from Baseline in the Patient's Assessment of Arthritis Pain (PtAAP) at Week 16

The change from Baseline at Week 16 in PtAAP will be analyzed as described in [Section 8.1.4.4](#).

8.2.1.12 Enthesitis-Free state based on Spondyloarthritis Research Consortium of Canada (SPARCC) index at Week 16

The SPARCC index measures the severity of enthesitis through the assessment of 16 sites, 8 for the right part and 8 for the left part of the body: the greater trochanter (right/left), quadriceps tendon insertion into the patella (right/left), patellar ligament insertion into the patella and tibial tuberosity (right/left), achilles tendon insertion (right/left), plantar fascia insertion (right/left), medial and lateral epicondyles (right/left), and the supraspinatus insertion (right/left). Tenderness on examination is recorded as either present (1) or absent (0) for each of the 16 sites, for an overall score range of 0 (no enthesitis) to 16 (severe enthesitis).

In case 9 or more are missing, the SPARCC index will be set to missing. If at least 8 items are available, the available items will be assessed and scored and then weighted by the number of the assessed items as shown in the formula below:

$$SPARCC\ index = n \times \frac{\sum_{i=1}^n score}{\sum_{i=1}^n AI}$$

where n refers to the number of total items and AI the number of assessed items.

The analysis of enthesitis-free state based on SPARCC index at Week 16 from Baseline will be restricted to the subset of subjects with enthesitis at Baseline (defined as SPARCC>0).

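### Enthesitis-free state (H7): prorating LEI has no effect at the LEI = 0 threshold, so sites not examined at Week 16 count as non-tender and can make a responder

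*SAP*

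**What the plan says.** Section 8.2.1.6 of the SAP defines LEI as six sites, each scored 0 or 1. On missing sites it says "In case 4 items are missing, the LEI will be set to missing", and then "If at least 3 items are available, the available items will be assessed and scored and then weighted" by the number of assessed items. The formula is n times the sum of scores divided by the number assessed, and "Note that n here refers to the number of total items", so n = 6. The responder definition follows: "Enthesitis-free state is based on a LEI response of 0 at Week 16", in subjects with LEI above 0 at Baseline. No sentence requires the sites that were tender at Baseline, or the same sites, to be examined at Week 16.

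Table 4-5 (Section 4.5) places this endpoint seventh in the fixed sequence, on pooled PA0010 and PA0011 data. Section 8.2.1.12 uses the same construction for the 16-site SPARCC index: "If at least 8 items are available, the available items will be assessed and scored and then weighted". SPARCC-free state is a secondary endpoint outside the hierarchy.

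For binary endpoints in the hierarchy, Section 4.2.1.1 states: "Further missing data for subjects on treatment, or data observed while not on treatment is also imputed to non-response". Section 4.2.2.1 applies NRI to subjects with missing data at the time point and, for ACR50, when the response cannot be derived from the available components.

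**The concern.** Proration is a reasonable device for a score analysed as a mean: it gives an unexamined site the average of the examined ones. At a threshold of zero it does nothing, because the prorated score is zero whenever the examined sites are clear, however many others were left out. The rule therefore amounts to scoring up to three unexamined sites as non-tender.

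ACR50 (Section 8.1.1) and MDA (Section 8.2.2) are handled differently. There a response needs enough available components to establish it, and undetermined cases go to NRI. Enthesitis-free state has no such safeguard, because an LEI from three sites counts as available.

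At stake is whether the H7 responder count includes subjects whose resolution was never observed. The planned NRI, modified composite and observed-case analyses all take the prorated LEI as given, so none of them would show the problem.

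**Working it through.** **Inputs.** Six LEI sites, at least three needed, LEI = 6 × sum / number assessed, response if LEI = 0 (Section 8.2.1.6). Assumed rates of 55% on bimekizumab (BKZ) and 39% on placebo, odds ratio 1.91, power 69%, 25% of subjects with Baseline enthesitis (Section 2.4.2). PA0010 arms of 420 and 280 (Section 2.3.1).

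**The plan's own figures.** The odds ratio reproduces: (0.55/0.45)/(0.39/0.61) = 1.91. The 69% power cannot be confirmed, because the size of PA0011 is not in the SAP. PA0010 alone (105 versus 70 subjects with enthesitis) gives 48% with the continuity correction. If PA0011 is assumed to add 400 subjects at 2:1, the pooled 172 versus 103 give 69.0%.

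**Mechanism.** Take a subject with both Achilles sites tender at Baseline and only the other four sites examined at Week 16, all clear. LEI = 6 × 0/4 = 0, a responder. With three sites examined and clear, LEI = 6 × 0/3 = 0.

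**Direction.** One tender site among 5, 4 or 3 examined gives 6/5 = 1.2, 6/4 = 1.5 or 6/3 = 2.0, never 0. Partial examination can create false responders but not false non-responders.

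**Size per affected subject.** If k sites are still tender and m of the 6 are missing at random, the chance that all k are among the missing is C(m,k)/C(6,k):

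| Sites missing | 1 tender | 2 tender | 3 tender |
|---|---|---|---|
| 1 | 1/6 = 17% | 0 | 0 |
| 2 | 2/6 = 33% | 1/15 = 7% | 0 |
| 3 | 3/6 = 50% | 3/15 = 20% | 1/20 = 5% |

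For SPARCC with 8 of 16 sites missing: 8/16 = 50% with one tender site and 28/120 = 23% with two.

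**Effect on the comparison.** Let a fraction q of subjects in each arm be partly examined, and let a fraction s of the true non-responders among them be converted. The observed rate is p + (1 − p)qs, so the difference becomes 16 × (1 − qs) points. It shrinks, because placebo has more true non-responders to convert. With s = 0.5 (three sites missing, one still tender) and the assumed 172 versus 103 subjects:

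| q | Difference (points) | Power |
|---|---|---|
| 0 | 16.0 | 69.0% |
| 1% | 15.9 | 68.4% |
| 2% | 15.8 | 67.9% |
| 5% | 15.6 | 66.5% |
| 10% | 15.2 | 64.1% |

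The values of q, s and the PA0011 size are assumptions; the SAP gives none of them.

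**The case against.** A reader might infer that the SAP contradicts its own NRI rule. It does not. Section 4.2.1 treats LEI as a single continuous measurement, Section 4.2.2.1 applies NRI at the level of the derived endpoint, and an LEI from three or more sites is by definition not missing. The conflict is with the purpose of NRI.

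A reader might also infer that the rule inflates H7 in favour of BKZ. The documents do not support that. Equal partial assessment dilutes the difference, as shown above. A bias towards BKZ would need more partial assessment on BKZ than on placebo, and nothing in the SAP suggests it.

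The strongest defence is that item-level substitution is a convention throughout the SAP. Joint counts are prorated with up to half the joints missing, PASI is completed with up to two of four regions missing, and HAQ-DI is scored from six of eight categories. This stands in part: the components of ACR50 and MDA may themselves be prorated, so the contrast with those endpoints holds at component level only. It does not answer the specific point, which is that at a zero threshold the weighting has no effect.

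Two further points stand. The one cause of missing LEI that the SAP names, remote visits during COVID-19 (Section 5.2), leaves the whole index missing, so NRI applies. And SPARCC-free state has nominal p-values only, so it adds nothing to the argument about H7.

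**Conclusion.** The derivation in Section 8.2.1.6 lets unexamined sites count as non-tender in a confirmatory responder endpoint, and no other section prevents it. The misclassification runs one way, towards false responders.

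Its size can be stated only per affected subject: up to 50% for one still-tender site and up to 20% for two, assuming sites are missing at random. The total effect depends on how often LEI is partly assessed, which the SAP does not give. If that is rare, the effect on H7 is small, and under equal missingness it works against the sponsor. That is not harmless: stated power is only 69%, and failure at H7 stops testing of H8 and H9. This is a gap in a derivation rule that is cheap to close, not evidence that the H7 result would be biased towards BKZ.

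**What to change.** In Section 8.2.1.6, derive enthesitis-free state directly from the sites:

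- Response only if all 6 sites were examined at Week 16 and none is tender. A weaker alternative requires only that every site tender or not assessed at Baseline was examined and that no examined site is tender; this would still miss a newly tender site that was not examined.
- Non-response if any examined site is tender.
- Otherwise missing, so that NRI gives non-response.

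Apply the same rule to the PA0011 data in the pooled analysis and to SPARCC-free state in Section 8.2.1.12. Report the number of partial assessments at Week 16 by arm. Keep proration for change from Baseline in LEI and SPARCC.

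The cost is SAP wording and a small programming change; the site scores are already needed for the formula. The downside is that a few subjects who have truly resolved but have an unexamined site become non-responders, which is the same price NRI already accepts elsewhere.
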